**Improving Walking in Peripheral Artery Disease**  
**ClinicalTrials.gov Identifier (NCT Number): NCT05103280**

## VA Tennis Shoes Protocol

**Title:** Improving Walking in Peripheral Artery Disease, Using Specially Designed Assistive Shoes

**Objective:** The objective of this research is to evaluate the ability of different **specially designed tennis shoes** to improve walking performance, muscle oxygenation of patients with peripheral artery disease (PAD).

**Hypothesis:** We hypothesize that the specially designed tennis shoes will provide assistance to the ischemic legs of patients with PAD and will therefore reduce the biological contribution and oxygen requirements of the ischemic leg muscles. This will acutely increase the walking performance, muscle oxygenation in the patients.

If our hypothesis is correct, the carbon fiber insole shoes and spring shoes may become a new effective conservative intervention for patients with PAD. However, if none of the components of our hypothesis are correct, then our study would direct us away from the carbon fiber insole shoes and/or spring shoes and toward other therapies.

We also hypothesize that an intervention with specially designed tennis shoes (spring loaded or carbon fiber insole shoes) will increase physical activity, and improve walking performance and quality of life. Our preliminary results show promising results in increasing the walking distances including initial claudication distances and absolute claudication distances during first-time use of the specially designed tennis shoes. Subjects will complete a 3month intervention with their preferred specially designed tennis shoe based on the initial data collection. They will be tested prior to starting the intervention and after 3 months of the intervention.

**Endpoints measured:** The patients will walk while wearing their own walking shoes, the carbon fiber insole shoes and the spring-loaded shoes (in random order) and we will measure the following performance endpoints for both phases:

- 1) **Initial and maximum claudication distance on our instrumented treadmill using the Gardner protocol:** Subjects will complete a Gardner treadmill walking. Subjects will walk in a dynamic gait and pressure analysis treadmill (FDMT Scifit AC500M, Noraxon USA, Inc., Scottsdale Ariz) located at the VA Medical center at Omaha. This treadmill collects synchronized pressure measurements allowing for gait analysis and the calculation of steps taken during exercise. Participants initiated exercise at 2.0 miles per hour at 0.0% incline. With each subsequent 2-minute stage, the treadmill incline was increased 2.0% to a maximum of 12.0%. Time of initial symptoms (claudication onset time [COT] and time at which claudication symptoms were prohibitive to further walking [peak walking time] will be recorded. Data will be collected using regular shoes and specially designed (carbon fiber insole shoes and spring) shoes. They will be allowed to rest for 15 minutes between tests. Patients will do 3 walks in the treadmill (regular walking shoes, carbon fiber insole shoes, and spring shoes).

2) **Calf muscle saturation at one-minute walking:** Bilateral gastrocnemius muscle oxygenation (StO2) will be measured using continuous-wave near infrared spectroscopy (PortaMon, Artinis Medical System, Netherlands) before, during and after each treadmill walking condition (described above). Measurements will be continuously captured during the exercise and recovery interval. We will measure resting StO2 and StO2 at 1-minute walking.

3) **Vertical ground reaction forces in the first two minutes of walking:** Biomechanical data will be collected with a dynamic gait and pressure analysis treadmill (FDMT SciFit AC5000M, Noraxon USA, Inc.). The parameter measured will be the vertical ground reaction force.

4) We will use the Borg Rating of Perceived Exertion (RPE) questionnaire after each condition

5) **Physical Activity:** Participants will wear the Actigraph (Actigraph GT3X, Actigraph, FL, USA) accelerometer on their hip for seven days (the whole day except when sleeping) prior to starting the intervention phase to measure baseline activity level and seven days after the intervention phase to measure post-intervention physical activity. Average steps/day, maximum cadence, and average peak activity index will be calculated.

6) **Questionnaires:** At the end of the study subject will be interviewed and asked to fill out survey questionnaires to assess acceptability, demand, implementation, and practicability. This interview will be held via phone call.

**Research Design:** This study will be a prospective clinical trial.

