### **Methodology:**

Recruit 30 willing patients with peripheral vascular disease and claudication at the vascular surgery clinic at the Nebraska and Western Iowa Veterans Affairs Medical Center (VANWIHCS) in Omaha. 10 patients will be recruited from the total 30 patients for the intervention phase and rest of the 20 patients will only participate in the baseline phase. Patients will be evaluated by a Board-Certified Vascular Surgeon to determine if they have PAD and whether they are eligible to participate in the study the study. Subject will be consented prior to the study.

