For statistical analysis, a linear mixed modeling approach (or generalized linear mixed model, as appropriate) will be used. This approach will allow us to detect differences within and between groups (different types of assistive shoes), and adjust for confounding variables. The main comparison of interest will be changes in walking distances due to wearing the assistive shoes. This pilot study will allow us to detect if walking distances improve after wearing the assistive shoes for 3-months. To evaluate the relationship between improvements in walking performance, physical activity, and quality of life, multiple correlations will be used. The level of significance will be set at  $p=0.05$ .

Outcome measure	Mean 1	Mean 2	Difference	Standard Deviation	Power	Required Sample Size
Push-off 	1.4	1.7	-0.3	0.30	0.79	29
Visual analog scale 	5.0	7.0	-2.0	2.00	0.81	30
Borg (scenario 2) 	14.0	11.0	3.0	2.50	0.81	23

Assumptions for sample size calculations to obtain 80% power. The test statistic is a two-sided paired t-test with an assumed correlation between mean 1 and mean 2 of 0.30. The alpha level is assumed as 0.001 to account for multiple comparisons between the different shoe types. Mean 1 is assumed as normal walking the control shoe and mean 2 is walking in the best assistive shoe. Choosing the largest sample size across all measures will ensure the desired power for all outcome measures\*.

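### The initial walks that guide the choice of the 3-month shoe are the only pre-intervention walks described; reused as that shoe's baseline, they could bias its change downward

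*Combined protocol and SAP*

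**What the plan says.** All references are to the combined protocol and SAP.

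- **Choice of shoe (Hypothesis).** "Subjects will complete a 3month intervention with their preferred specially designed tennis shoe based on the initial data collection". The text does not say what makes a shoe preferred: walking distance, comfort, perceived exertion or the subject's wish.
- **Test times (Hypothesis).** "They will be tested prior to starting the intervention and after 3 months of the intervention". It is not stated whether the test before the intervention is the initial session or a new one.
- **Treadmill walks (Endpoints measured).** "Patients will do 3 walks in the treadmill (regular walking shoes, carbon fiber insole shoes, and spring shoes". No repeat walk in any shoe is described. The introduction to the endpoint list says "we will measure the following performance endpoints for both phases". The only pre-intervention measurement described separately is seven-day accelerometry, worn "prior to starting the intervention phase to measure baseline activity level".
- **Numbers (Methodology).** "10 patients will be recruited from the total 30 patients for the intervention phase"; the other 20 take part in the baseline phase only.
- **Analysis (Statistical Analysis, intervention paragraphs).** The aim is stated as "This pilot study will allow us to detect if walking distances improve after wearing the assistive shoes for 3-months". The mixed model is also meant to "detect differences within and between groups (different types of assistive shoes". The shoe worn at each time point of the main comparison is not named, and the analysis does not mention how the shoe was chosen.

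**The concern.** Suppose a subject is given the shoe in which he walked further, and that walk is also his baseline. The baseline was then selected partly for a favourable test error. On retest the error averages zero, so the expected change is negative even if nothing has changed. The 3-month question is whether walking distance improves, so the error works against the hypothesis under test: a real gain may be hidden, or a decline reported where there is none.

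A second problem does not depend on the baseline. In the intervention phase no one is randomized to a shoe; each subject wears the one he prefers. A 3-month difference between carbon fiber and spring shoes therefore mixes the effect of the shoe with the kind of subject who chose it.

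**Working it through.** **Inputs from the plan.** Intervention-phase sizing: N = 30, 0.59 SD, alpha 0.025, 80% power, paired t-test. Planned number after the intervention: 10. Analysis alpha: 0.05. Correlation between conditions: 0.30, given in the note to the sizing table for push-off, visual analog scale and Borg, not for walking distance.

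**Assumptions.** The documents do not give the test error of the walking test, the true difference between shoes, or the share of subjects whose choice follows performance. These are varied below.

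**1. The plan's own figure.** Exact noncentral-t power of a two-sided paired t-test, with 0.59 in SDs of the paired difference, N = 30 and alpha 0.025: 80.2%. The stated 80% reproduces. On the same basis, N = 10 gives 26.5% at alpha 0.025 and 38.5% at alpha 0.05 without any selection.

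**2. Worst-case bias.** Two shoes have equal true means, all within-person variation is test error, the longer walk decides, and that walk is reused as baseline. With correlation ρ and unit SD per condition:

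- Inflation of the chosen baseline = √((1 − ρ)/π). At ρ = 0.30: √(0.70/3.1416) = 0.472 SD. At ρ = 0.80: √(0.20/3.1416) = 0.252 SD.
- SD of the paired difference = √(2(1 − ρ)). At ρ = 0.30: √1.40 = 1.183. At ρ = 0.80: √0.40 = 0.632.
- Ratio: 0.472/1.183 = 0.399 and 0.252/0.632 = 0.399. In general it is 1/√(2π) = 0.40.

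So the worst case is 0.40 SD of the paired difference whatever the correlation. A true gain of 0.59 SD would average 0.59 − 0.40 = 0.19 SD.

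**3. Consequences and range.** Simulation of a paired t-test, n = 10, two-sided alpha 0.05. Bias and gain are in SDs of the pre-post difference in the chosen shoe.

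| Assumption | Bias | False decline, no true change | Power for a 0.59 SD gain |
|---|---|---|---|
| Worst case | −0.40 | 23% | 9% |
| Half of within-person variance is a stable person-by-shoe difference | −0.28 | 13% | 15% |
| Three quarters stable | −0.20 | about 8% | 20% |
| One shoe truly better by 1 SD of the difference | −0.24 | about 10% | about 17% |
| Half of subjects choose by performance | −0.20 | 9% | 20% |
| Choice unrelated to test error, or a new baseline walk | 0.00 | 2.5% | 39% |

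At N = 30 and alpha 0.025, the plan's sizing scenario, the worst case lowers power from 80% to about 12.6%.

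**4. Own-shoe reference.** In the worst-case model, month-3 chosen shoe minus baseline own shoe shows a bias of 0.00. Where person-by-shoe differences are stable the contrast is positive (0.235 per-condition SD at ρ = 0.30 with half the variance stable). That is a real advantage of wearing the better-suited shoe, not regression to the mean.

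**The case against.** The strongest reply is that the bias needs three conditions, none of them stated: that preference tracks measured walking, that the choosing walk is reused as baseline, and that the contrast is pre-post within the same shoe. Preference may rest on comfort or on the Borg rating taken after each walk. The test before the intervention may be a new session. The intervention-phase sizing speaks of walking with and without the assistive shoes, which could mean an own-shoe reference, and against that reference the bias is absent. The 0.59 SD was also not stated for a same-shoe contrast.

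This reply stands against a stronger reading, that the 3-month change is certainly biased. A reader might infer it, but the documents do not settle any of the three conditions. The reply does not remove the point. The Methodology treats the initial session as the baseline phase, no second pre-intervention treadmill session is described, and the sizing-table note refers to the best assistive shoe. Reuse is therefore the most natural way to carry out the plan, and choice by performance is plausible.

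A reader might also infer that a biased pilot estimate would set the size of the later study. The documents do not say so. They already give 30 subjects and 0.59 SD, and say only that further funding will be sought to reach full power.

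On the second problem, the plan's general adjustment for confounding variables is not an adequate answer: with 10 subjects in total, it cannot be relied on to separate shoe from chooser.

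**Conclusion.** The point holds as a conditional one. The plan does not separate the data that choose the 3-month shoe from the data that may serve as its baseline. If choice tracks walking performance and the walk is reused, the same-shoe change is biased downward, by at most about 0.40 SD of the paired difference under the models tried. The 23% false decline and 9% power belong to that ceiling. They are not predictions for this trial, and the bias falls to zero under the last row of the table. Expressed per condition, the ceiling is 0.47 SD at a correlation of 0.30, which is an assumption for walking distance.

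The self-selection of the 3-month shoe groups needs none of these conditions. It follows from assigning shoes by preference and holds whichever baseline is used.

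**What to change.** - State that the walk used to choose the shoe is not that shoe's pre-intervention value.
- Use the own-shoe baseline walk as the reference. It plays no part in choosing between the two assistive shoes. Report two contrasts: month-3 own shoe minus baseline own shoe, and month-3 preferred shoe minus baseline own shoe.
- Note beside the second contrast that it combines the immediate effect of the shoe with the effect of three months of wear. The first contrast is reported alongside it for that reason.
- Report shoe-versus-shoe results at 3 months as descriptive only.

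**Cost.** Wording only. The own-shoe baseline walk is already collected, and own-shoe walking at month 3 is within the plan as the endpoint introduction reads, since it lists all three shoes for both phases. No extra treadmill test is needed. What is given up is a clean estimate of change within the preferred shoe.

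### Resting calf StO2 is recorded before every walk but has no stated role in the StO2 endpoint or its model; pre-specifying it as a covariate would gain precision at almost no cost

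*Combined protocol and SAP*

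**What the plan says.** All places are in the combined protocol and SAP.

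- **Endpoint.** Endpoints measured, item 2, opens with "Calf muscle saturation at one-minute walking: Bilateral gastrocnemius muscle oxygenation (StO2) will be measured using continuous-wave near infrared spectroscopy". Recording takes place "before, during and after each treadmill walking condition", so each walk has its own resting value on each leg. The item ends with "We will measure resting StO2 and StO2 at 1-minute walking". It does not say whether the analysed quantity is the one-minute value, the change from rest, or the one-minute value adjusted for rest.
- **Walks.** Item 1 has three treadmill walks, one per shoe, each taken to the claudication limit: "time at which claudication symptoms were prohibitive to further walking [peak walking time] will be recorded". Between walks, "They will be allowed to rest for 15 minutes between tests". No return of StO2 to its resting level is required before the next walk.
- **Order.** The paragraph introducing the endpoints says that the shoes are worn in random order.
- **Analysis.** The Statistical Analysis section plans a linear or generalized linear mixed model with adjustment for confounders. It lists none of them and mentions neither StO2 nor test position.

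**The concern.** Muscle oxygenation is one of the two outcomes named in the Objective. The Hypothesis is that the shoes lower the oxygen requirement of the ischemic leg muscles. One minute into the first treadmill stage (2.0 mph, no incline), StO2 reflects where the calf started and how far it has moved since. The hypothesis concerns the second part, so the one-minute value given its own starting value is closer to the question than the one-minute value alone.

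Two of the three walks start 15 minutes after a walk to the claudication limit. If recovery differs between patients or between walks, starting levels vary within a patient for reasons unrelated to the shoe, and that variation enters the shoe contrast as noise. A test-position term removes the average shift between walks but not each patient's own departure from it. The resting value recorded before the same walk can remove part of that.

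There is also a pre-specification gap. Three analysis variables remain open once the data are seen, and they can differ considerably in precision.

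**Working it through.** **No plan figure to reproduce.** The documents give no StO2 mean, standard deviation, correlation, effect size or power. The stated power figures concern push-off, a visual analog scale, Borg, or no named outcome.

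**Inputs.** 30 patients (Methodology); 3 walks each in random order (Endpoints measured). Assumed: a within-patient correlation ρ between resting and one-minute StO2 across walks, taken as 0, 0.3, 0.5 and 0.7; equal within-patient SDs for the two values; one leg per patient for simplicity.

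**Step 1. Variance of a shoe contrast, relative to the one-minute value alone.**

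- Change from rest: 2(1 − ρ).
- Adjusted for rest: (1 − ρ²) × [1 + 1/(f − 2)], where f is the within-patient error degrees of freedom before the covariate enters. With shoe in the model, f = 90 − 30 − 2 = 58, so the bracket is 1 + 1/56 = 1.018. With test position also in the model, f = 56 and the bracket is 1 + 1/54 = 1.019.

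| ρ (assumed) | One-minute value | Change from rest | Adjusted for rest |
|---|---|---|---|
| 0 | 1 | 2.00 | 1.02 |
| 0.3 | 1 | 1.40 | 0.91 × 1.018 = 0.93 |
| 0.5 | 1 | 1.00 | 0.75 × 1.018 = 0.76 |
| 0.7 | 1 | 0.60 | 0.51 × 1.018 = 0.52 |

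A simulation of 30 patients and three walks in random order, using patient-centred least squares with and without a position term (4,000 runs per setting), gave ratios within about 0.015 of the last column.

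At ρ = 0.5 the adjusted analysis of 30 patients is worth about 30/0.763 = 39 patients analysed without the covariate. That figure comes entirely from the choice of ρ.

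**Step 2. Does incomplete recovery bias the shoe contrast?** Suppose walks two and three are shifted by c (in SD units) whatever shoe came before. Under random order each shoe has probability 1/3 of coming first. The shift in a patient's difference between two shoes is then +c, 0 or −c with probability 1/3 each: its mean is 0 and its SD is c√(2/3). Averaged over 30 patients, the SD of the chance imbalance is c√(2/3)/√30.

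| c (assumed) | Expected bias | SD added per patient | SD of chance imbalance, n = 30 |
|---|---|---|---|
| 0.25 | 0 | 0.20 | 0.04 |
| 0.5 | 0 | 0.41 | 0.07 |
| 1.0 | 0 | 0.82 | 0.15 |

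A simple recovery effect therefore costs precision and does not shift the expected contrast. An effect that depends on which shoe was worn on the preceding walk is a different case and could bias the contrast. The documents give nothing from which to judge it.

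**The case against.** The strongest reply is that the plan is silent rather than wrong, and much of that reply stands.

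- A reader might infer that the endpoint is the absolute one-minute StO2 and that the resting value is discarded. The documents do not say so. Item 2 names both values in one sentence, and change from rest is a possible reading. The unnamed confounders could also include resting StO2. What can be said is that the heading names the one-minute value and that nothing commits to using the resting one.
- A reader might infer that the shoe effect is confounded with recovery. Random order answers this for a simple order or recovery effect, as step 2 shows.
- Nothing in the documents shows that 15 minutes is too short for calf StO2 to recover. If resting values return to the same level before every walk, the recovery argument falls away, and the gain rests on whatever other walk-to-walk correlation remains.
- The variance factors are close to 1 − ρ² for an assumed ρ. They show what could be gained, not what will be.
- The factors are for the within-patient slope and one leg per patient. A raw resting value in a random-intercept model can blend between-patient and within-patient slopes, and item 2 measures both legs. The covariate must be set up accordingly.

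None of this removes the case for the change. With no correlation the loss is about 2%, and with a moderate or high one the gain is substantial. Change from rest is less precise than the unadjusted value whenever ρ is below 0.5.

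**Conclusion.** The point holds as a matter of precision and pre-specification. The plan names the one-minute value, collects a resting value before each walk, gives that value no stated role, and does not mention StO2 in the analysis section. Relative to the one-minute value alone, adjustment multiplies the shoe-contrast variance by between about 1.02 (ρ = 0) and 0.52 (ρ = 0.7). This rests on assumed correlations and, for the comparison with change from rest, on equal SDs. The actual gain cannot be determined from the documents. They do not support a claim that the planned contrast is biased or that the rest period is inadequate. The change is worth making before analysis because the data are already to be collected.

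**What to change.** State in the Statistical Analysis section that the StO2 outcome is the one-minute value, analysed in a linear mixed model with:

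- shoe and test position as factors;
- patient and leg within patient as random effects;
- resting StO2 taken before that same walk on that same leg as a covariate, split into the leg's own mean over its walks and the walk's deviation from that mean, so that the within-patient slope does the adjusting.

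Since the two legs share each walk, the model should also allow for their correlation on the same walk (for example, a random effect for walk within patient), so that they are not counted as independent replicates of the shoe.

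Report the unadjusted one-minute value as a sensitivity analysis.

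**Cost.** A few lines of SAP text and one or two degrees of freedom for the covariate. No new measurement, visit or procedure is needed.

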**Background:**

Peripheral Arterial Disease (PAD) affects approximately 8.5 million of people age 40 and older in the United States according to the CDC (Benjamin 2019). Intermittent claudication (IC) is the most common presentation of PAD. Intermittent claudication presents as cramping pain, occurring in the calves, thighs and/or buttocks brought on by physical activity and relieved with rest (Myers 2016). This impairment is of major importance primarily because it restricts the physical activity of PAD patients, leading to further adverse effects on their general health and quality of life (Hernandez 2019). Recently IC has been identified as an ambulatory disorder. Previous studies done by our group demonstrate that patients with clinically diagnosed femoro-popliteal PAD have significant ankle motion alterations with abnormal ankle joint kinematics. Celis et al demonstrate that PAD patients had evidence of significant ambulatory abnormalities even when not experiencing any claudication pain. The abnormalities contributing to the baseline gait dysfunction are complex and include axonal nerves loss (Koopman1996)(Laghi1996) and mitochondrial dysfunction (Pipinos2007)(Pipinos2006)(Pipinos2000). Ischemia superimposed to this issue would then result in variability worsening gait resulting in an increased work requirement and energy cost.

Despite the functional limitations present in PAD, only few medical therapies exist for improving walking performance and preventing mobility loss in patients with PAD. Exercise training has been demonstrated to improve PAD symptoms and is recommended as first line therapy for PAD. The carbon fiber insole tennis shoe is designed with a full-length, carbon fiber plate underfoot that is supposed to provide a propulsive sensation to help to push the pace. Hoogkamer et al reported that this tennis shoe lowered the energetic cost of running by 4% on average (Hoogkamer 2018). The spring-loaded shoe has a shock-absorbing springs in the soles that relieve the stress and fatigue from athletic activities. In this study, we want to evaluate the effectiveness of these two specially designed tennis shoes and determine if they improve walking performance and/or reduce walking work requirement in PAD patients compared to regular walking shoes.

